13.3.12.1 Immediate Evaluation for Potential Skin ECIs

A. Photographs:

Every attempt should be made to get a photograph of the actual ECI skin lesion or rash as soon as possible. **Obtain appropriate consent for subject photographs if a consent form addendum is required by your IRB/ERC.**

- Take digital photographs of:
 - the head (to assess mucosal or eye involvement),
 - the trunk and extremities, and
 - a close-up of the skin lesion/rash.
- If possible, a ruler should be placed alongside the site of a skin occurrence as a fixed marker of distance.
- The time/date stamp should be set in the 'ON' position for documentation purposes.
- Photographs should be stored with the subject's study records.
- The Drug Manufacturer may request copies of photographs. The local study contact (e.g., CRA) will provide guidance to the site, if needed.

B. Past Medical History:

Collect past medical history relevant to the event, using the questions in Appendix 2 (Past Medical History Related to Dermatologic Event) as a guide. Any preexisting conditions not previously reported (e.g., drug allergy) should be entered into the Medical History eCRF.

C. Presentation of the Event:

Collect information on clinical presentation and potential contributing factors using the questions in Appendix 3 (Presentation of the Dermatologic Event) as a guide. This information should be summarized and entered in narrative format in the AE eCRF. Please use the available free-text fields, such as Signs and Symptoms. Note pertinent negatives where applicable to reflect that the information was collected. Any treatments administered should be entered on the Concomitant Medication eCRF.

D. Vitals Signs and Standard Laboratory Tests:

Measure vital signs (pulse, sitting BP, oral temperature, and respiratory rate) and record on the Vital Signs eCRF. Perform standard laboratory tests (CBC with manual differential and serum chemistry panel, including LFTs).

E. Focused Skin Examination:

Perform a focused skin examination using the questions in Appendix 4 (Focused Skin Examination) as a guide. Information should be summarized and entered on the Adverse Experience eCRF as part of the narrative.

F. Dermatology Consult

Refer the subject to a dermatologist as soon as possible.

- For a “**severe rash**”, the subject must be seen within **1-2 days** of reporting the event.
- For **clinically significant rash**, the subject should be seen within **3-5 days**.

The dermatologist should submit a biopsy sample to a certified dermatopathology laboratory or to a pathologist experienced in reviewing skin specimens.

The site should provide the dermatologist with all relevant case history, including copies of clinical photographs and laboratory test results.

13.3.13 Other

The following AEs, regardless of grade, are considered ECIs and should be reported to the Drug Manufacturer within 24 hours of the event:

- Myocarditis
- Pericarditis
- Pancreatitis
- Any additional Grade 3 or higher event which the physician considers to be immune related

All attempts should be made to rule out other causes. Therapeutic specialists should be consulted as appropriate. However the AE should be reported regardless of etiology.

Course of Action

Grade 2 events or Grade 1 events that do not improve with symptomatic treatment:

- Withhold pembrolizumab.
- Systemic corticosteroids may be indicated.
- Consider biopsy for confirmation of diagnosis.
- If pembrolizumab held and corticosteroid required, manage as per grade 3 below.

Grade 3 events:

- Hold pembrolizumab
- Treat with systemic corticosteroids at a dose of 1 to 2 mg/kg prednisone or equivalent once per day.
- When symptoms improve to Grade 1 or less, steroid taper should be started and continued over no less than 4 weeks.
- Permanently discontinue for inability to reduce corticosteroid dose to 10 mg or less of prednisone or equivalent per day within 12 weeks. Otherwise, pembrolizumab treatment may be restarted and the dose modified as specified in the protocol

Grade 4 events:

- Treat with systemic corticosteroids at a dose of 1 to 2 mg/kg prednisone or equivalent once per day.
- Discontinue pembrolizumab

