6.2.1.2 Dose Modification

Pembrolizumab will be withheld for drug-related Grade 4 hematologic toxicities, non-hematological toxicity \geq Grade 3 including laboratory abnormalities, and severe or life-threatening AEs as per Table 3 below.

Table 3: Dose modification guidelines for drug-related adverse events.

Toxicity	Grade	Hold Treatment (Y/N)	Timing for restarting treatment	Dose/Schedule for restarting treatment	Discontinue Subject (after consultation with Drug Manufacturer)
Hematological Toxicity	1, 2	No	N/A	N/A	N/A
	3* *Excluding Grade 3 neutropenia, anemia, and thrombocytopenia	Yes	Toxicity resolves to Grade 0-1 or baseline	May increase the dosing interval by 1 week	Toxicity does not resolve within 12 weeks of last infusion
	4	Yes	Toxicity resolves to Grade 0-1 or baseline	May increase the dosing interval by 1 week	Permanent discontinuation should be considered for any severe or life-threatening event
Non-hematological toxicity	1	No	N/A	N/A	N/A
	2	Consider withholding for persistent symptoms	Toxicity resolves to Grade 0-1 or baseline	Clinical AE resolves within 4 weeks: Same dose and schedule (reference Section 5.6.1.2 for recommendations regarding pneumonitis) Clinical AE does not resolve within 4 weeks: May increase the dosing interval	Toxicity does not resolve within 12 weeks of last infusion

Note:
Exception to be treated similar to grade 1 toxicity

- Grade 2 alopecia
- Grade 2 fatigue

Toxicity	Grade	Hold Treatment (Y/N)	Timing for restarting treatment	Dose/Schedule for restarting treatment	Discontinue Subject (after consultation with Drug Manufacturer)
For additional information regarding Adverse Events with a potential Immune-Etiology reference Section 5.6.1.1.				by 1 week for each occurrence	
	3, 4	Yes	Toxicity resolves to Grade 0-1 or baseline	May increase the dosing interval by 1 week for each occurrence	Toxicity does not resolve within 12 weeks of last infusion Permanent discontinuation should be considered for any severe or life-threatening event

In case toxicity does not resolve to Grade 0-1 within 12 weeks after last infusion, trial treatment should be discontinued after consultation with the PI. With PI agreement, subjects with a laboratory adverse event still at Grade 2 after 12 weeks may continue treatment in the trial only if asymptomatic and controlled. For information on the management of adverse events, see Section 13.3.

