Subjects who experience a recurrence of the same severe or life-threatening event at the same grade or greater with re-challenge of pembrolizumab should be discontinued from trial treatment.

Table 3 Dose Modification and Toxicity Management Guidelines for Immune-related AEs Associated with Pembrolizumab

General instructions:				

 1. Corticosteroid taper should be initiated upon AE improving to Grade 1 or less and continue to taper over at least 4 weeks. 2. For situations where pembrolizumab has been withheld, pembrolizumab can be resumed after AE has been reduced to Grade 1 or 0 and corticosteroid has been tapered. Pembrolizumab should be permanently discontinued if AE does not resolve within 12 weeks of last dose or corticosteroids cannot be reduced to ≤ 10 mg prednisone or equivalent per day within 12 weeks. 3. For severe and life-threatening irAEs, IV corticosteroid should be initiated first followed by oral steroid. Other immunosuppressive treatment should be initiated if irAEs cannot be controlled by corticosteroids. 				
Immune-related AEs	Toxicity grade or conditions (CTCAEv4.0)	Action taken to pembrolizumab	irAE management with corticosteroid and/or other therapies	Monitor and follow-up
Pneumonitis	Grade 2	Withhold	
 • Administer corticosteroids (initial dose of 1-2 mg/kg prednisone or equivalent) followed by taper 	
 • Monitor participants for signs and symptoms of pneumonitis • Evaluate participants with suspected pneumonitis with radiographic imaging and initiate corticosteroid treatment • Add prophylactic antibiotics for opportunistic infections
	Grade 3 or 4, or recurrent Grade 2	Permanently discontinue		

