Hypothyroidism	Grade 2-4	Continue	
 Initiate thyroid replacement hormones (eg, levothyroxine or liothyronine) per standard of care 	
 Monitor for signs and symptoms of thyroid disorders.
Nephritis and Renal dysfunction	Grade 2	Withhold	
 Administer corticosteroids (prednisone 1-2 mg/kg or equivalent) followed by taper. 	
 Monitor changes of renal function
	Grade 3 or 4	Permanently discontinue		
Myocarditis	Grade 1 or 2	Withhold	
 Based on severity of AE administer corticosteroids 	
 Ensure adequate evaluation to confirm etiology and/or exclude other causes

	Grade 3 or 4	Permanently discontinue		
All other immune-related AEs	Intolerable/ persistent Grade 2	Withhold	
Based on type and severity of AE administer corticosteroids	
Ensure adequate evaluation to confirm etiology and/or exclude other causes
	Grade 3	Withhold or discontinue based on the type of event. Events that require discontinuation include and not limited to: Gullain-Barre Syndrome, encephalitis		
	Grade 4 or recurrent Grade 3	Permanently discontinue		

1. Withhold or permanently discontinue pembrolizumab is at the discretion of the investigator or treating physician.
 
NOTE:
 
For participants with Grade 3 or 4 immune-related endocrinopathy where withhold of pembrolizumab is required, pembrolizumab may be resumed when AE resolves to \leq Grade 2 and is controlled with hormonal replacement therapy or achieved metabolic control (in case of T1DM).
				

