8.1.5.2 Treatment Period

8.1.5.2.1 Re-initiation of therapy after treatment interruption (Retreatment / Second Treatment Course)

Subjects are allowed to stop pembrolizumab with SD or better if the below conditions are met. Such patients may be eligible for up to one year of additional pembrolizumab therapy if they progress after stopping pembrolizumab (Second Treatment Course). This is only available if the study remains open and the subject meets the following conditions:

Either

- a. Stopped initial treatment with pembrolizumab after attaining an investigator determined confirmed CR
- b. Was treated for at least 24 weeks with pembrolizumab before discontinuing therapy
- c. Received at least two treatments with pembrolizumab beyond the date when the initial CR was declared

OR

Subject had SD, PR or CR and stopped pembrolizumab treatment after 24 months of study therapy for reasons other than disease progression or intolerability

AND

- a. Experienced an investigator-determined confirmed radiographic disease progression after stopping their initial treatment with pembrolizumab
- b. Did not receive any anti-cancer treatment since the last dose of pembrolizumab
- c. Has a performance status of 0 or 1 on the ECOG Performance Scale
- d. Demonstrates adequate organ function as detailed in Section 6.1.2
- e. Female subject of childbearing potential should have a negative urine or serum pregnancy test within 72 hours prior to receiving retreatment with study medication.
- f. Female subjects of childbearing potential should be willing to use 2 methods of birth control or be surgically sterile, or abstain from heterosexual activity for the course of the study through 120 days after the last dose of study medication (please see Section 6.9.2 for details).
- g. Male subjects should agree to use an adequate method of contraception starting with the first dose of study therapy through 120 days after the last dose of study therapy.
- h. Does not have a history or current evidence of any condition, therapy, or laboratory abnormality that might interfere with the subject's participation for the full duration of the trial or is not in the best interest of the subject to participate, in the opinion of the

treating investigator.

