Each of the events above is described within this guidance paragraph, along with site requirements for reporting these events to the Drug Manufacturer. The information collected should be entered into the narrative field(s) of the Adverse Event module in the database (please note, if narrative entry into the database is not available, please use the narrative text box on the 1727/AER Form). If additional Medical History or Concomitant Medications are reported, the Medical History and Concomitant Medication modules in the database must be updated.

In addition, the guidelines include recommendations on the management of these ECIs. These guidelines are intended to be applied when the physician determines the events to be

related to pembrolizumab. Note: if after the evaluation the event is determined not to be related, the physician is instructed to follow the ECI reporting guidance but does not need to follow the treatment guidance (below). Therefore, these recommendations should be seen as guidelines and the treating physician should exercise individual clinical judgment based on the patient. For any question of dose modification or other treatment options, the specific language in the protocol should be followed. Any questions pertaining to the collection of this information or management of ECIs should be directed to your local Drug Manufacturer contact.

Dose Modification/Discontinuation

The treatment guidance provides specific direction when to hold and/or discontinue pembrolizumab for each immune related adverse event. Of note, when the guidance states to “discontinue” pembrolizumab this is the permanent discontinuation of treatment with pembrolizumab. “Hold” means to stop treating with pembrolizumab but resumption of treatment may be considered assuming the patient meets the criteria for resumption of treatment (see Section 8.1.5.2.1).

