Thyroid disorders can occur at any time during treatment. Monitor patients for changes in thyroid function (at the start of treatment, periodically during treatment, and as indicated based on clinical evaluation) and for clinical signs and symptoms of thyroid disorders.

Grade 2 events (and Grade 3-4 hypothyroidism):

- Report as ECI if appropriate (see Table 1)
- Monitor thyroid function or other hormonal level tests and serum chemistries more frequently until returned to baseline values.
- Thyroid hormone and/or steroid replacement therapy to manage adrenal insufficiency.
- Therapy with pembrolizumab can be continued while treatment for the thyroid disorder is instituted.
- In hyperthyroidism, non-selective beta-blockers (e.g. propranolol) are suggested as initial therapy.
- In hypothyroidism, thyroid hormone replacement therapy, with levothyroxine or liothyronine, is indicated per standard of care.
- Consultation with an endocrinologist may be considered.

Grade 3 hyperthyroidism events:

- Report as ECI
- Hold pembrolizumab.
- Rule out infection and sepsis with appropriate cultures and imaging.
- Treat with an initial dose of methylprednisolone 1 to 2 mg/kg intravenously followed by oral prednisone 1 to 2 mg/kg per day. When symptoms improve to Grade 1 or less, steroid taper should be started and continued over no less than 4 weeks. Replacement of appropriate hormones may be required as the steroid dose is tapered.
- Permanently discontinue for inability to reduce corticosteroid dose to 10 mg or less of prednisone or equivalent per day within 12 weeks.

Grade 4 events:

- Report as ECI
- Discontinue pembrolizumab.
- Manage as per Grade 3

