13.3.7 Hematologic

The following AE term, if considered Grade ≥ 3 or requiring dose modification or use of systemic steroids to treat the AE, are considered an ECI and should be reported to the Drug Manufacturer within 24 hours of the event:

- Autoimmune hemolytic anemia
- Aplastic anemia
- Disseminated Intravascular Coagulation (DIC)
- Haemolytic Uraemic Syndrome (HUS)
- Idiopathic (or immune) Thrombocytopenia Purpura (ITP)
- Thrombotic Thrombocytopenic Purpura (TTP)
- Any Grade 4 anemia regardless of underlying mechanism

All attempts should be made to rule out other causes such as metastases, sepsis and/or infection. Relevant diagnostic studies such as peripheral blood smear, reticulocyte count, LDH, haptoglobin, bone marrow biopsy or Coomb's test, etc., should be considered to confirm the diagnosis. However the AE should be reported regardless of etiology.

Course of Action

Grade 2 events:

- Report as ECI
- Hold pembrolizumab
- Prednisone 1-2 mg/kg daily may be indicated
- Consider Hematology consultation.
Permanently discontinue for inability to reduce corticosteroid dose to 10 mg or less of prednisone or equivalent per day within 12 weeks.

Grade 3 events:

- Report as ECI
- Hematology consultation.
- Hold pembrolizumab Discontinuation should be considered as per specific protocol guidance.
- Treat with methylprednisolone 125 mg iv or prednisone 1-2 mg/kg p.o. (or equivalent) as appropriate
- Permanently discontinue for inability to reduce corticosteroid dose to 10 mg or less of prednisone or equivalent per day within 12 weeks.

Grade 4 events:

- Report as ECI
- Hematology consultation
- Discontinue pembrolizumab for all solid tumor indications; refer to protocol for hematologic malignancies.

- Treat with methylprednisolone 125 mg iv or prednisone 1-2 mg/kg p.o. (or equivalent) as appropriate

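### Section 6.2.1.2 and the guidance in Section 13.3 disagree on hold, discontinue or restart for a few events, most clearly Grade 3 myocarditis, and the guidance points to the wrong restart section

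*Combined protocol and SAP*

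**What the plan says.** Instructions on holding, stopping and restarting pembrolizumab stand in two places.

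Section 6.2.1.2 has two tables, both numbered Table 3. One covers drug-related adverse events in general; the other covers immune-related events. In the second, the myocarditis row withholds at Grades 1 and 2 and then reads "Grade 3 or 4 Permanently discontinue". Its general instructions add "Pembrolizumab should be permanently discontinued if AE does not resolve within 12 weeks of last dose". The text below the first table says "With PI agreement, subjects with a laboratory adverse event still at Grade 2 after 12 weeks may continue treatment", provided that the event is asymptomatic and controlled.

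Section 13.3 is the appended guidance on events of clinical interest. Section 13.3.13 lists myocarditis and, at Grade 3, asks for a hold and steroids. If the steroid cannot be brought down within 12 weeks, treatment ends; if it can, "Otherwise, pembrolizumab treatment may be restarted and the dose modified as specified in the protocol". For Grade 4 hematologic events, Section 13.3.7 says "Discontinue pembrolizumab for all solid tumor indications; refer to protocol for hematologic malignancies". Section 13.3.1 defines discontinuing as permanent. Of a hold it says that "resumption of treatment may be considered assuming the patient meets the criteria for resumption of treatment (see Section 8.1.5.2.1". Section 8.1.5.2.1 is the Second Treatment Course rule. One of its conditions is "Experienced an investigator-determined confirmed radiographic disease progression after stopping their initial treatment with pembrolizumab".

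**The concern.** A site that reads only the table and a site that reads only the appendix can reach different decisions for the same event and grade. For Grade 3 myocarditis the difference is between never giving the drug again and possibly giving it again. That is first a matter of patient safety.

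It also touches the data. Toxicity is a secondary objective, reported as incidence by type and severity. Treatment exposure and counts of discontinuation for adverse events would depend in part on which page a treating physician used.

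**Working it through.** There is no figure to recompute. The check compares the two tables of 6.2.1.2 with the guidance from 13.3.4 to 13.3.14 by event and grade, and then follows the restart cross-reference.

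1. **Myocarditis, Grade 3.** The immune-event table has a row for this event and permanently discontinues. Section 13.3.13 holds and allows a restart. Both name the event and the grade, so this is a direct contradiction.

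2. **Drug-related anemia, Grade 4.** The general table holds at Grade 4, allows restart on recovery to Grade 0-1 or baseline, and asks only that permanent discontinuation be considered. Section 13.3.7 includes every Grade 4 anemia whatever its cause, and discontinues. Section 13.3.1 applies its management advice to events judged related to the drug, so a drug-related Grade 4 anemia falls under both rules. If the anemia is classed as immune-related, the catch-all row of the immune-event table also discontinues at Grade 4 and agrees with 13.3.7.

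3. **Hyperthyroidism and hypophysitis, Grade 4.** The immune-event table leaves withholding or stopping to the physician at Grades 3 and 4. Its closing note allows a withheld patient with an endocrine event to resume at Grade 2 or lower with hormonal or metabolic control. Section 13.3.6 discontinues at Grade 4, which 13.3.1 makes permanent. The first text permits a restart that the second rules out. A drafting gap adds to this. The block in 13.3.6 headed "Grade 2 events (and Grade 3-4 hypothyroidism" lets treatment continue, but the later Grade 4 block under the same thyroid heading does not say that hypothyroidism is excluded.

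4. **Immune-related laboratory event, still Grade 2 at 12 weeks.** The text of 6.2.1.2 lets the patient continue with the principal investigator's agreement. The general instructions of the immune-event table call for permanent discontinuation if the event has not resolved by then. An immune-related Grade 2 transaminase elevation that is asymptomatic and controlled meets both. Both rules are in 6.2.1.2.

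5. **Restart after a hold.** Section 8.1.5.2.1 offers two routes. One requires stopping after a confirmed complete response, with at least 24 weeks of treatment and two doses after the response was declared. The other requires stopping after 24 months for reasons other than progression or intolerability. Both then require confirmed radiographic progression after stopping. An ordinary patient held for toxicity has not completed either route, and without progression fails the common condition. Restart rules suited to a toxicity hold are in 6.2.1.2: recovery to Grade 0-1 or baseline in the general table, recovery to Grade 0-1 with steroid tapered in the immune-event table, and the endocrine note. Section 13.3.1 cites none of them.

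**Where the texts agree.** The pneumonitis, diarrhea/colitis, hepatic and nephritis rows match 13.3.4, 13.3.5, 13.3.8 and 13.3.11 on hold versus discontinue.

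**The case against.** The best defence is precedence. Section 13.3.1 calls its recommendations guidelines and tells the reader to follow the protocol's specific language on any question of dose modification. Other sections describe 13.3 as a separate guidance document, and it carries its own version number. Section 6.2.1.2 refers to 13.3 for managing events, not for dose decisions. The restart sentence in 13.3.13 itself ends by deferring to the protocol. On this view the tables govern and the appendix gives way.

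This has weight: it is not established that two opposite decisions would both comply with the protocol. But it does not remove the conflict. Section 13.3 is bound into the protocol as an appendix, 6.2.1.2 sends the reader there, and 6.10 points to Section 13 for unacceptable adverse experiences as a reason to discontinue. The deferral is therefore circular. It also cannot settle item 4, which lies inside 6.2.1.2, and it does not say which of the two tables applies.

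Other objections succeed against wider readings that a reader might infer:

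- **Hypothyroidism, Grade 4, as a direct contradiction.** The block that continues treatment names it expressly, and the later Grade 4 block follows one on hyperthyroidism. The natural reading is an incomplete heading.
- **Hematologic events in general.** Most conditions listed in 13.3.7, when immune-related, fall under the catch-all row of the immune-event table. That row matches at Grade 4 and is compatible at Grade 3. At Grade 2 it differs only by requiring the event to be intolerable or persistent.
- **All laboratory events at 12 weeks.** For events that are not immune-related, only the exception in the text applies. Even for immune-related ones, the two rules could be read as a default and an exception, but the documents do not say so.
- **No restart rule at all.** Usable rules exist; the cross-reference misses them.
- **Mandatory against discretionary at Grade 4 endocrine events.** Discretion includes stopping, so the instructions are not opposite. They differ on whether resumption is possible.

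**Conclusion.** The point holds in limited form. There is one direct contradiction (Grade 3 myocarditis), three narrower mismatches (items 2 to 4) and one wrong cross-reference. It rests on reading 13.3 as part of the protocol and, for item 2, on the anemia being judged drug-related. A patient with a confirmed complete response who stopped and later progressed could satisfy 8.1.5.2.1, but that is not a toxicity hold.

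A reader might infer that the tables and the appendix conflict throughout, or that the primary analysis is at risk. The documents support neither. Major immune-event rows agree, and Section 6.11 counts any treated patient as evaluable, so the response-rate denominator does not depend on these rules. The toxicity analysis is descriptive. How many patients would be affected cannot be derived from the documents. The reason to act is patient safety at low cost.

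**What to change.** - Reconcile 6.2.1.2 (its text and both tables) with 13.3.6, 13.3.7 and 13.3.13 so that each event and grade in items 1 to 4 has one action.
- State in one sentence which table governs dose decisions, and give the two tables in 6.2.1.2 different numbers.
- Make the Grade 4 thyroid heading in 13.3.6 say which conditions it covers.
- State how the 12-week exception for laboratory events relates to the general instructions of the immune-event table.
- In 13.3.1, replace the reference to 8.1.5.2.1 with the section that the sponsor intends to govern restart after a toxicity hold.

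The choice of clinical rule in each case belongs to the sponsor's clinicians; this review takes no position on it. The cost is a clinical review and an amendment to one section and one appendix. Sample size and analysis are unaffected.
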